## Postoperatively:

- Must be admitted to the general pediatric floor postoperatively (versus intensive care unit)
- On POD #1 in the morning, patients in both groups will be visited by the research assistant. Patients in the VR arm will be offered the VR device for up to 30 minutes, and patients in the control arm will be offered an iPad for up to 30 minutes
- Number of hours since anesthesia end will be recorded
- Pain scores (FACES scale by the patient, FLACC scores by the research assistant) will be recorded immediately prior to intervention (T=0) and at end of intervention (T=30); FLACC score by research assistant will also be recorded at 10 minute mark (T=10)
- PCA use (in mcg or mg as appropriate) for previous hour prior to intervention (T=-60-0), during intervention (T=0-30), and one hour after intervention is complete (T=30-90) will be recorded; PCA use will be converted to morphine equivalents at time of data entry
- Total number of minutes of electronic device use will be recorded. The electronic device will be applied for a total of 30 minutes maximum, after which time the session will end
- On POD #1 in the afternoon, research assistant will return for patients in both groups, for another session up to 30 minutes. Data for both groups will be recorded as above

	If a patient declines to participate, the reason for declining will be asked for and recorded
	
 
Post-intervention:         
 
Patients and caregivers in the VR group will be given a survey regarding acceptance and effectiveness of the VR device in the postoperative period at approximately 48-72 hours
 
Patients and caregivers in both groups will be given a follow-up survey at approximately 48-72 hours and 7-10 days
 
Surveys will be conducted by phone, email or in person
 
 
 

Subject Population	Inclusion Criteria
key criteria for Inclusion	1. Subjects age 11 – 17
and Exclusion:	
 
Patients undergoing idiopathic scoliosis surgery on ERAS spine protocol (which includes postoperative PCA)
 
No contraindication to using an iPad or VR device
 

	Exclusion Criteria
	1. Patient/caregiver refusal
	2. Patients with developmental delay
	3. Patients with seizure disorder
	4. Non-English-speaking patients
	5. Patients with daily opioid use ≥ two weeks
	6. Patients with uncorrected visual or hearing impairment
	7. Patients admitted to pediatric intensive care unit on POD#1

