## Study phases are as follows:

Screening/Consent/Baseline: Randomization and consent will be obtained preoperatively. A baseline anxiety score will be assessed on a self-report form (STAI short form). Patients in the VR arm will be oriented to the VR device before surgery. All patients will be oriented to the Wong-Baker FACES pain scale. Baseline pain scores will be obtained through the following method: FACES scale (patient reported) and FLACC score (measured by the trained research assistant). Baseline vital signs will be measured and recorded. The STAI, FACES, and FLACC scoring tools have all been used and previously validated in the pediatric population.

Intervention/Treatment: On postoperative day (POD) #1 in the morning, patients in both groups will be visited by the research assistant. Standardized scripts will be utilized by the research assistant for the entirety of the data collection. Patients in the VR arm will be offered the VR device for up to 30 minutes. Patients in the control arm will be offered an iPad for up to 30 minutes. After a total of 30 minutes maximum, the session will end. Routine data will be collected on pain scores and PCA use as below for both groups. On POD #1 in the afternoon, a research assistant will return for patients in both

groups, for another session of the respective electronic device for up to 30 minutes. If a patient declines to participate, the reason for declining will be asked for and recorded.

In the control arm of the study, the iPad will have a variety of vetted and screened games available. The content on the iPads will include puzzles, games, and movies that have been previously vetted and approved by the Child Life team, separate from this study, and are currently used as standard of care at UNC. The Child Life team is an integral part of pediatric postoperative recovery at UNC.

In the VR arm of the study, there will be selected programs to choose from. All of the content will be pleasant games or exploring programs, avoiding unpleasant and fast-moving settings such as fighting or racing. All of the content will be age appropriate, vetted and screened by the research team for violence or otherwise stressing scenarios, content requiring rapid eye motion or head movement, and content requiring more body movement than what can comfortably be done in a sitting or reclined position.

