Both iPads and VR devices are interactive (regardless of fingers versus head movement) and this type of movement difference should not confound results. Our study aims to assess whether the VR immersive experience provides superior distraction to the standard of care (iPad use), thus by nature of the study design we are studying the difference in the two distinct types of experiences. Finger versus head movement use is inherent to the types of distraction and central to the distinct experiences. Similarly, there will be different apps between VR and iPad platforms by nature of the differences in platforms. Our goal is to examine whether an immersive experience is more beneficial than an iPad-based experience, rather than examine specific styles of games.

There will be no restriction to personal electronic use. Both groups will have access to their personal devices (cell phones, iPads) as is the standard of care. The study iPad will only be offered at specific times as designated twice a day on POD#1 for participants in the control group. Outside of the study windows, participants will not be provided with hospital iPads. Personal electronic devices including iPads are acceptable, as is the standard of care for patients to bring whatever they see fit into the hospital.

There will be a variety of popular games and apps, deemed to be content- and age-appropriate by the Child Life specialists. Program offerings will not vary by specific age or gender; our study will only include ages 11-17 and per discussion with Child Life the programs do not need to be subdivided to remain appropriate within this age range.

Standard of care for both groups will include PCA use as ordered by the surgical team as well as routine Child Life visits. The Child Life team is an integral part of pediatric postoperative recovery at UNC.

The following will be recorded: Number of hours since anesthesia end. Pain scores including FACES scale by the patient and FLACC scores by the research assistant will be recorded immediately prior to intervention (T=0) and at end of intervention (T=30); FLACC score will also be recorded at the 10 minute mark (T=10). PCA use, in mcg or mg as appropriate, for the hour prior to intervention (T=-60-0), during intervention (T=0-30), and one hour after intervention is complete (T=30-90) will be recorded. Total number of minutes of electronic device use will be recorded. PCA use will be converted to morphine equivalents at time of data entry.

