#### **Exclusion Criteria:**

- Patient/caregiver refusal
- Patients with developmental delay
- Patients with seizure disorder
- Non-English-speaking patients

- Patients with daily opioid use ≥ two weeks
- · Patients with uncorrected visual or hearing impairment
- Patients admitted to pediatric intensive care unit on POD#1

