## 5 STUDY EVALUATIONS AND MEASUREMENTS

- Variables that will be abstracted from the medical charts:
  - Name, medical record number, phone number
  - Age (years), gender (male or female), race or ethnicity, weight (kg), BMI (kg/m2), heart rate (0-200 beats/min), and blood pressure (0-250/0-150 mmHg) pre-operatively
  - Surgery type, current medications
  - Pain scores, vital signs
  - Intraoperative record
- o Baseline evaluation will include chart review, by phone or in person assessment for inclusion and exclusion criteria, vital sign assessment, study consent and orientation.
- Preoperatively, baseline vital signs will be obtained and recorded by nursing staff per UNC standard of care practices. Additionally, two pain scores will be assessed: FACES by the patient and FLACC by the research assistant.
- O Postoperatively, pain scores including FACES scale by the patient and FLACC scores by the research assistant will be recorded immediately prior to intervention (T=0) and at end of intervention (T=30); FLACC score will also be recorded at the 10 minute mark (T=10). PCA use, in mcg or mg as appropriate, for the hour prior to intervention (T=-60-0), during intervention (T=0-30), and one hour after intervention is complete (T=30-90) will be recorded. Total number of minutes of electronic device use will be recorded. This data will be recorded by the research assistant.
- o PCA use will be converted to morphine equivalents at time of data entry.

Descriptions of each questionnaire and scale, including total score computations:

Short State-Trait Anxiety Inventory (STAI) – 6 statements (i.e., 'I feel calm', with 1=Not at all, 2=Somewhat, 3=Moderately, 4=Very much). Scores 6-24, with 6 signifying no anxiety and 24 points signifying the highest level of anxiety. This short form of the STAI was used and validated in children aged 5-16 years (Schisler et al, 1998; Apell et al, 2011)

FACES (Wong-Baker) Pain Rating Scale – Self-assessment scale; patients select a face that illustrates the pain they are experiencing. Scores 0-10, with 0=No hurt and 10=Hurts worst (wongbakerfaces.org)

FLACC (Face, Legs, Activity, Cry, Consolability) – Observer assessment scale, with 5 categories (i.e., 'Face', with 0=No particular expression or smile, 1=Occasional grimace or frown, 2=Frequent to constant quivering chin, clenched jaw). Scores 0-2 in each category, for total scores 0-10, with 0=No observed pain and 10=Most observed pain

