## **6 STATISTICAL CONSIDERATIONS**

#### 6.1 Primary Outcomes

Postoperative pain scores and postoperative PCA opioid usage surrounding intervention (in morphine equivalents).

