#### **6.3 Statistical Methods**

All statistical estimates (e.g., means, medians, proportions, incidence rates, mean differences, correlations, etc.) will be tabulated along with corresponding confidence intervals (CIs). To avoid overreliance on p-values, the magnitudes of estimates and the corresponding confidence intervals will be the primary focus of the analyses. Quantitative data analysis will occur using SAS or R and will be conducted under the supervision of a UNC Department of Anesthesiology biostatistician along with other members of the UNC Department of Anesthesiology research division.

We will work closely with our departmental statistician in all statistical analyses. After discussion with our biostatistician, we do plan to utilize a completely randomized study design. For our post-study analysis, we will perform analyses with and without gender stratification to assess whether gender is a contributing factor in opioid usage and pain scores.

For Aim 1 (comparing postoperative pain and anxiety scores), the following questionnaires and scales with validated scoring as above will be analyzed: short STAI, FACES, FLACC, PHBQ-AS.

For Aim 2 (comparing postoperative opioid usage), opioid usage will be converted into morphine equivalents at the time of data entry and analyzed.

For Aim 3 (assessing patient and caregiver satisfaction), qualitative satisfaction will be documented, divided into positive and negative comments. Patient satisfaction and overall experience are commonly linked to pain experienced during a hospitalization, and as a result, satisfaction with the use of VR as a method of pain control will be one of our outcomes.

We hypothesize that the use of virtual reality programs will provide superior distraction to standard of care and will result in improved pain scores and reduced opioid consumption after surgery. We will utilize two-sample t-test to compare the pain scores and opioid consumption in VR and control groups.

We will have the p-values reported and Bonferroni correction will be used to adjust for multiple comparison. P-values not reaching the significance level will be deemed as inconclusive.

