# 7 STUDY INTERVENTION (drug, device or other intervention details)

The Applied VR is a lightweight mobile virtual reality headset with embedded software, creating an immersive experience. The Applied VR is specifically designed for medical use. The devices will be stored in a locked room within the Department of Anesthesiology. There will be no modifications to the packaging or labeling of the devices, as this may interfere with the application and functionality of the devices. During the intervention phase of the study, a research assistant will be monitoring the patients to assist with technical issues with the device, as well as to monitor for compliance and adherence.

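### Assistant-rated FLACC counts among the primary pain scores with no masked rater, so rater expectation could shift the estimated VR effect, although every eligible patient already self-reports pain on FACES.

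*Combined protocol and SAP*

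**What the plan says.** Section 6.1 lists the primary outcomes as "Postoperative pain scores and postoperative PCA opioid usage surrounding intervention (in morphine equivalents"; section 4.2 lists the same two. Neither names a pain scale, session or time point. The content of the pain scores has to be read from other sections:

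- Section 3.1 (study phases): "Pain scores including FACES scale by the patient and FLACC scores by the research assistant will be recorded", before the intervention (T=0) and at its end (T=30).
- Synopsis, postoperative procedures: "FLACC score by research assistant will also be recorded at 10 minute mark (T=10"). FACES is not collected at that time.
- Section 5 describes FLACC as an "Observer assessment scale, with 5 categories", each scored 0-2, for a total of 0-10.
- Section 6.3, Aim 1: "the following questionnaires and scales with validated scoring as above will be analyzed: short STAI, FACES, FLACC, PHBQ-AS". The two-sample t-test is then applied to the pain scores and opioid consumption, with a Bonferroni correction.

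On who does what, section 3.1 says that "patients in both groups will be visited by the research assistant" and that VR or the iPad is offered at that visit. Section 7 adds that "a research assistant will be monitoring the patients to assist with technical issues with the device", and that this person also checks compliance and adherence.

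On blinding, sections 3.1 and 3.2 concern patients only: the device is not disclosed at consent, and private areas before and after surgery keep them from learning about the other arm. Section 3.1 also requires standardized scripts throughout data collection, and the FLACC rater is described as trained.

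On self-report, patients are 11-17 years old and all are oriented to FACES. The exclusions include "Patients with developmental delay", non-English speakers, and uncorrected visual or hearing impairment.

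**The concern.** One component of the primary pain outcome is a judgement made by study staff who, as the plan is written, can see which device the patient has. Sections 2 and 6.3 state the team's expectation that VR will be superior, so any unconscious leniency has an obvious direction. Section 3.2 takes deliberate steps against bias on the patient's side because of public interest in VR. Nothing comparable is provided for the person scoring FLACC.

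More than a p-value is at stake. Section 6.3 puts estimates and confidence intervals first, and section 6.4 says the pilot is to supply the effect size for the primary outcome. A systematic rater shift goes straight into that estimate and could carry into the planning of a later trial. The exposure is also avoidable: a patient-reported score is already planned at T=0 and T=30 for everyone.

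**Working it through.** **Step 1. Is FLACC primary?** Sections 4.2 and 6.1 say pain scores. Sections 3.1 and 5 say pain scores include FACES and FLACC. Section 6.3 analyses both for the pain aim. Nothing makes FLACC secondary, so as written it is part of the primary outcome.

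**Step 2. Does the rater know the arm?** The documents do not say so directly. But the research assistant scores FLACC at T=10, during a session in which the patient has been given a headset or an iPad. Device help and adherence checks fall to the same role, and no separate or masked rater is named. Masking is not feasible at T=10 as written, and is not provided for at T=0 or T=30.

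**Step 3. Is an observer scale needed?** The age range, the exclusions and universal orientation to FACES mean that every eligible patient is expected to self-report. FACES is already scheduled at T=0 and T=30.

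**Step 4. Effect on the estimate.** Let b be the amount by which FLACC is scored lower in the VR arm because of expectation. Then

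expected observed difference = true difference - b (VR minus control).

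Sample size does not enter. A larger trial narrows the interval around the wrong value.

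**Step 5. Effect on the test (illustration only).** The plan has no power calculation, so there is no figure to reproduce.

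- From the documents: 10 completed patients per arm (3.3); two-sample t-test and Bonferroni (6.3).
- Assumed: SD 1, 1.5 or 2 FLACC points; b = 0.5 or 1 point; true effect zero; one FLACC reading per patient; two-sided alpha 0.05, 0.025 (two tests) or 0.0125 (four tests). The plan states neither alpha nor the number of comparisons.

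Degrees of freedom = 10 + 10 - 2 = 18. Noncentrality = b / (SD × √(2/10)) = (b/SD) × √5.

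- b = 0.5: SD 2 gives 0.25 × 2.236 = 0.559; SD 1.5 gives 0.745; SD 1 gives 1.118.
- b = 1: SD 2 gives 1.118; SD 1.5 gives 1.491; SD 1 gives 2.236.

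Critical values of t with 18 df are 2.101, 2.445 and 2.775 at the three alphas. The probability that a noncentral t exceeds them, in the direction favouring VR, is:

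| Two-sided alpha | No bias | b = 0.5: SD 2 / 1.5 / 1 | b = 1: SD 2 / 1.5 / 1 |
|---|---|---|---|
| 0.05 | 2.5% | 7.6% / 10.5% / 18.4% | 18.4% / 29.2% / 56.2% |
| 0.025 | 1.25% | 4.3% / 6.1% / 11.5% | 11.5% / 19.7% / 43.6% |
| 0.0125 | 0.6% | 2.4% / 3.5% / 7.0% | 7.0% / 12.9% / 32.5% |

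Because section 6.3 specifies Bonferroni, the lower two rows are closer to the plan than the first. The correction lowers the error rates but does nothing about the shift in step 4.

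**The case against.** The strongest reply is that this is a 20-patient pilot in which FLACC is not the sole basis for any conclusion. FACES stands beside it at T=0 and T=30, PCA use is a second primary outcome that the rater does not judge, and section 6.3 treats non-significant results as inconclusive. FLACC is described as validated, the assistant is trained, and scripts are standardized. This limits the severity. But scripts and training standardize conduct without hiding the arm, validation of a scale does not protect against an unmasked rater, and a pilot meant to yield an effect size is damaged by a biased estimate.

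Several stronger readings are tempting, and the documents do not support them:

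- A reader might infer that one individual delivers the device and rates every score. The text uses both *the* and *a* research assistant. It supports a shared role with no separate rater, not a single person.
- A reader might infer that blinding ends entirely at consent. Section 3.2 also withholds information about the other arm after surgery. That protects against comparison by patients; it does not mask the rater.
- A reader might infer that a false VR benefit will occur, or take the rates at alpha 0.05 as the plan's own error rates. The existence, direction and size of any bias are unknown, and the plan corrects for multiplicity.
- A reader might infer that collecting FACES before FLACC keeps the two scores independent. It stops FLACC prompting FACES, but an assistant who sees the FACES answer can still be influenced by it when scoring FLACC.
- A reader might infer that demoting FLACC automatically eases the Bonferroni correction. Section 6.3 does not confine the correction to primary outcomes.

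**Conclusion.** The point holds at moderate strength. As written, an observer score from a role that can see the allocation is part of the primary pain outcome, with no masked rating, in patients who all provide a self-report. Rater expectation could shift the FLACC difference, and the pilot's effect-size estimate, by its full amount at any sample size.

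The false-positive rates are conditional on assumed SDs and biases: 2-18% for a 0.5-point shift and 7-56% for a 1-point shift across the three alphas. They show sensitivity; they do not predict what this trial will find. That the rater is unmasked and that all patients can self-report are inferences, but firm ones. The change should be made; the concern does not invalidate the trial.

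**What to change.** - In 4.2 and 6.1, name patient-reported FACES at T=30 as the primary pain score. Because POD#1 has a morning and an afternoon session, each with its own T=30, state how they are used, for example the mean of the two T=30 scores.
- Move FLACC at all time points to secondary, labelled as rated by an unblinded assessor and not used alone to support efficacy.
- State in 3.2 that the research assistant is not blinded to arm.
- If fewer tests are to be claimed as a benefit, say in 6.3 that the Bonferroni family is limited to the primary comparisons and list them.

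The cost is protocol wording only, with no added rater, visit or data item. The downside is that FLACC no longer contributes to the primary claim. FACES also remains an open-label self-report, so patient expectation is not removed; only the rater's judgement is taken out of the primary pain estimate.

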## 3 INVESTIGATIONAL PLAN

#### 3.1 Study Design

This will be a randomized controlled pilot study comparing virtual reality to standard electronic use after pediatric idiopathic scoliosis surgery. Patients age 11-17 years old undergoing idiopathic scoliosis surgery will be included. Patients will be randomized to either the virtual reality or control (iPad) group. The randomization-and-concealment feature of REDCap data capture system will be utilized.

Subject eligibility will be verified by the research coordinator through chart review and patient questionnaire prior to enrollment in the study. The patients will be blinded to their study arm until they agree to be part of the study. Participants will be properly oriented to their respective device (VR or iPad) before surgery. While the use of VR may be new to the patients, VR is a very popular, trending and mainstream concept that is not likely to be unfamiliar to patients in the study age group. The patients will have the ability to stop using the VR device at any time if they choose.

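### Pain scores and PCA windows are timed both by the session and by the clock, and the two disagree whenever a session ends before 30 minutes

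*Combined protocol and SAP*

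**What the plan says.** Section 3.1 makes 30 minutes a maximum in both arms. The VR arm is described this way: "Patients in the VR arm will be offered the VR device for up to 30 minutes". The iPad session has the same ceiling. For VR it adds: "The patients will have the ability to stop using the VR device at any time if they choose". Early discontinuation is a secondary outcome, for VR in section 4.2 and for either device in section 6.2.

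The same section gives most measurements two anchors, one in words and one on the clock:

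- Pain scores "will be recorded immediately prior to intervention (T=0) and at end of intervention (T=30".
- The first PCA window after the start: "during intervention (T=0-30".
- The second PCA window: "one hour after intervention is complete (T=30-90) will be recorded".

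The exception is the mid-session observer score, which is fixed by the clock in both its words and its label: "FLACC score will also be recorded at the 10 minute mark (T=10". The synopsis (postoperative procedures) and the measurement list at the start of section 5 repeat the double anchoring.

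One place differs. The units-of-measurement paragraph in section 5 lists PCA use by clock interval only (-60 to 0, 0 to 30 and 30 to 90 min) and lists device minutes as a separate variable. It gives no time for the pain scores.

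Pain scores and PCA use around the intervention are the primary outcomes (sections 4.2 and 6.1). Section 6.3 compares them by two-sample t-test. It states no adjustment for window length and no use of the recorded device minutes.

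**The concern.** The words and the clock labels give the same time only if the session lasts exactly 30 minutes. For any shorter session, no rule says which one governs. One research assistant could score pain and close the first PCA window when the device comes off. Another could wait until minute 30, and both would be following the protocol. If a patient stopped at 8 minutes, the session reading would even put the final score before the 10-minute FLACC.

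PCA use is recorded as an amount, so a shorter window gives a smaller figure at the same rate of use. Stopping early happens after randomization and could differ between devices. Section 1.3 acknowledges a small risk of motion sickness and nausea with VR, and section 5.3 gives that kind of risk as the reason for the 30-minute limit. If windows follow the session, the length of observation for a primary outcome can depend on the assigned arm.

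This matters in a pilot because section 6.3 puts the weight on the size of the estimates, and section 6.4 says the data will be used to estimate the effect on the primary outcome. An artefact of window length would enter that estimate and could carry into later planning.

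**Working it through.** **The plan's own figure.** The post-session window is called one hour and labelled 30 to 90: 90 − 30 = 60 min, ending 30 + 60 = 90 min after the start. This reproduces, but only for a session of exactly 30 min.

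**One session stopped at d minutes.**
- Clock reading: windows of 30 and 60 min, total 90 min, whatever d is.
- Session reading: the during window runs from 0 to d, the post window from d to d + 60 (still 60 min, but earlier), and the total is d + 60.

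| d (min) | During window | Fall, 1 − d/30 | Total, d + 60 | Fall, 1 − (d + 60)/90 |
|---|---|---|---|---|
| 30 | 30 | 0% | 90 | 0% |
| 20 | 20 | 33.3% | 80 | 11.1% |
| 15 | 15 | 50.0% | 75 | 16.7% |
| 10 | 10 | 66.7% | 70 | 22.2% |

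**Arm level, session reading.** The documents give no stopping rates, so the shares here are assumptions. Let a share f of VR sessions stop at d, let all iPad sessions last 30 min, and let PCA use per minute be equal in both arms. The mean VR during window is m = f·d + (1 − f)·30.

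| f, d | m (min) | During amount, 1 − m/30 | Total to end + 60, 1 − (m + 60)/90 |
|---|---|---|---|
| 20% at 10 min | 0.2·10 + 0.8·30 = 26 | 13.3% lower | 1 − 86/90 = 4.4% lower |
| 30% at 10 min | 0.3·10 + 0.7·30 = 24 | 20.0% lower | 1 − 84/90 = 6.7% lower |
| 50% at 15 min | 0.5·15 + 0.5·30 = 22.5 | 25.0% lower | 1 − 82.5/90 = 8.3% lower |

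If the pre-session hour is added to the total (150 min when nobody stops early), the falls are 4/150 = 2.7%, 6/150 = 4.0% and 7.5/150 = 5.0%.

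**Other stopping patterns.** With equal stopping in both arms, the mean windows are equal and there is no bias. If 30% of iPad sessions and no VR sessions stop at 15 min, the iPad mean is 0.3·15 + 0.7·30 = 25.5 min. VR then appears 30/25.5 − 1 = 17.6% higher in the during window.

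**Effect on the planned t-test.** This was simulated with 10 patients per arm, 40,000 runs, no true difference, a log-normal PCA rate, a two-sided 5% level (the plan states none) and VR stops at 15 min. The coefficient of variation (CV) is assumed. The nominal rate of false findings in favour of VR is 2.5%.
- During window, CV 0.5: 6.4%, 9.9% and 22.2% when 20%, 30% and 50% of VR sessions stop.
- Total to end + 60, CV 0.5: 3.3%, 3.9% and 5.3%.
- During window, 30% stopping: from 17.1% (CV 0.3) to 6.2% (CV 0.8).
- Equal windows: 2.1% to 2.5%, close to nominal.

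**Pain.** Under the session reading the score is taken at d instead of at 30 min. The documents give no course of pain over time, so neither the size nor the direction of any bias can be calculated.

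**The case against.** The strongest reply is that section 5 largely settles the opioid half. Its units paragraph gives PCA windows in clock minutes, without session wording, and keeps device minutes apart. Every T label elsewhere is also numeric, so the natural reading is a clock schedule with descriptive words for a nominal 30-minute session. This carries weight, and it shows which way the sponsor leans. It does not remove the session wording from section 3.1, the synopsis and the measurement list in section 5, and it says nothing about the pain score.

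A second reply is that no passage makes the during window the endpoint. The outcome is PCA use around the intervention, and over a longer total the artefact is small. That is right, and it is why both sets of figures are shown. The plan also does not say whether the windows are summed, so the larger figures cannot be ruled out.

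Third, recorded device minutes would expose uneven stopping and would allow the during amount to be turned into a rate. That is true, but no such step is planned, and it would not recover a FACES score that was not taken at minute 30.

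Fourth, scoring pain when the device comes off is a defensible choice in a distraction study. It is, but it measures something different from a score at a fixed time, and the plan should say which one it compares.

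Finally, this is a pilot of 20 completed patients that treats non-significant results as inconclusive. That limits the harm from a false positive test, but not from a distorted effect estimate.

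**Conclusion.** The ambiguity is real. The two anchors conflict for every session shorter than 30 minutes, the protocol allows and expects such sessions, and only the PCA windows have a clock-only definition anywhere. If staff follow the session wording and early stopping differs by arm, the opioid comparison is biased. In the illustrative cases where only VR sessions stop early, the size is 13% to 25% for the during window and 4.4% to 8.3% for the total to one hour after the session. These figures rest on assumed stopping patterns and on equal, constant PCA rates.

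A reader might infer more than this, and the documents do not support it:

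- *That an early stop necessarily shortens the opioid window and moves the pain score.* This happens only under the session reading; under the clock reading neither occurs.
- *That the post-session hour is cut short.* It moves earlier but stays 60 minutes.
- *That the wording produces a false VR benefit.* That needs more or earlier stopping on VR. Equal stopping gives no bias, earlier iPad stopping reverses it, and section 6.2 anticipates stopping on either device.
- *That pain is biased in a known direction.* Nothing in the documents allows one to be derived.

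This is a cheap improvement to make before data collection.

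**What to change.** Bring section 3.1, the synopsis and the measurement list in section 5 into line with the units paragraph in section 5:

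- Count PCA windows as -60 to 0, 0 to 30 and 30 to 90 minutes from session start in both arms, whatever the device minutes. Remove the session-based wording attached to them.
- Take the FACES and FLACC scores used for the comparison at 30 minutes from session start in both arms, whether or not the device is still on. A score at device removal may be kept as an additional descriptive measure.
- Keep device minutes as a separate variable.

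Each patient then contributes 30 + 60 = 90 minutes after the start for any session length, and the window-length artefact is zero. The cost is a wording change, plus the research assistant staying or returning at minute 30 when a session ends early.
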